Ages and Stages Questionnaire, Third Edition (ASQ-3) Autism spectrum disorder (ASD) Autism Diagnostic Observation Schedule, Second Edition (ADOS-2) Child Behavior Checklist (CBCL) Developmental Delay (DD) Diagnostic and Statistical Manual of Mental Disorders, Fifth Edition (DSM-5) Early Evaluation (EE) Modified Checklist for Autism in Toddlers (M-CHAT) Mullen Scales of Early Learning (MSEL) Primary care physician (PCP) Pupillary light reflex (PLR) Research Electronic Data Capture (REDCap) Screening Tool for Autism in Toddlers (STAT) Vineland Adaptive Behavior Scale, Third Edition (VABS-3)

1.0 Background & Rationale

(A) Significance

Autism spectrum disorder (ASD) is a complex, highly heritable neurodevelopmental disability with recent prevalence estimates of 1 in 59 children [1] and lifetime costs exceeding \$2.4 million [2]. Families of young children across the nation face significant barriers to accessing timely, local early ASD diagnostic evaluations, ultimately delaying entry into evidence-based interventions, which have the potential to improve outcomes [3] and lower societal costs [4]. As such, federal agencies (e.g., National Institute of Mental Health), advisory committees (e.g., Interagency Autism Coordinating Committee), and investigators and stakeholders in the field of ASD research [5] are collectively calling for studies that evaluate the diagnostic accuracy of streamlined assessment models, determine the accuracy of novel biomarkers for the classification of ASD in populationbased samples, and examine whether these tools may be feasibly implemented along with existing clinical assessment within primary care settings to improve diagnostic classification accuracy. To date, researchers have independently examined community-based models of early ASD diagnosis [6-9] and measures of underlying biological processes [10] as alternative approaches to identifying children with ASD. However, given the complex, heterogeneous nature of the ASD phenotype, multi-method community-based evaluation approaches that integrate both clinical and biobehavioral tools have the potential to improve the accuracy and timeliness of early ASD diagnosis [5].

Overall Scientific Premise

There is consensus among ASD experts that symptoms emerge in the first year of life and the disorder can be reliably identified during the toddler years [11]. Yet, nationally the average age of ASD diagnosis is not until 4 to 5 years [5], with diagnosis of children from lower income, minority, and rural families lagging an additional year and a half [12-14]. Clinical guidelines for ASD diagnosis support the use of multidisciplinary team assessment [15]; however, a shortage of expert providers leads to long wait times and travel burden for families of young children and significant strain on the public health care system. Most critically, the significant delay between the emergence of ASD symptoms and diagnosis means that young children are missing critical

opportunities for early, evidence-based interventions at the time of optimal neuroplasticity. The current proposal addresses this need by linking a community-based clinical evaluation model with the utilization of biobehavioral markers to test the diagnostic efficacy of these approaches for accurately classifying young children with ASD in a high-risk community-referral sample in the primary care setting.

Scientific Premise for Aim #1

Pediatric advocacy groups [16] have highlighted the challenges around access to early diagnostic services for children at risk for ASD and have called for the evaluation of new models of care delivery [5]. To date, three small studies have investigated whether training community-based clinicians to provide ASD diagnostic services is a feasible endeavor. McClure and colleagues [7] trained local teams of health professionals to perform ASD assessment. Of 33 children evaluated, there was 87% diagnostic agreement with the expert ASD evaluation team and a significant reduction in wait time for evaluations. Warren and colleagues [9] reported on a program in which pediatricians were trained to diagnose young children with ASD in community practice settings. In this pilot study of 21 children ages 22-37 months, there was 71% agreement between pediatrician diagnosis and independent expert ASD evaluation. In follow-up to this work, Swanson and colleagues [8] used the same training model to measure the accuracy of ASD diagnostic evaluation in a sample of 14 children with 86-93% diagnostic agreement between local pediatric providers and independent expert evaluation. Limitations to these important preliminary studies include small sample sizes and limited variability in child diagnosis (including under representation of those ultimately diagnosed with ASD and those with co-occurring intellectual disability) and baseline level of knowledge in community providers. Yet, these studies represent promising preliminary evidence for implementation of innovative models in which local pediatric health professionals provide ASD diagnostic evaluations in community settings. The proposed project builds on this preliminary evidence by testing an existing statewide model of early ASD diagnosis in the primary care setting with a high-risk community-referral sample of children. We will determine the diagnostic validity of this existing model by comparing diagnostic agreement between primary care providers and independent expert ASD evaluation.

Scientific Premise for Aim #2

Prospective, longitudinal studies of high-risk infants have begun to yield potential risk factors, or *biomarkers*, of infants later diagnosed with ASD. These biomarkers have the potential to elucidate the mechanisms that contribute to the development of ASD, ultimately providing methods for earlier identification of the disorder and potential early intervention targets. Neuroimaging methods, such as structural magnetic resonance imaging (MRI) measures [17-19] and electroencephalography (EEG) [20-22], have been utilized to study early neural markers of ASD. However, it remains unclear whether these are appropriate tools to be used with infants, children, and lower-functioning individuals, because obtaining high-quality data from these groups can be extremely difficult. To date, the most non-invasive, low-cost, and feasible approach to identifying early risk factors for ASD may be the use of eye-tracking technology.

Several brief, easy to administer eye-tracking indices of neuromodulator activity have been shown to be sensitive to ASD. For example, Nyström and colleagues [23] reported that pupillary light reflex (PLR), which is associated with the neurotransmitter acetylcholine (Ach) [24], differed between 9- to 10-month-old high-risk infants later diagnosed with ASD compared to both high-

and low-risk infants that did not, and was associated with ASD symptom severity at 36 months. Anderson and colleagues [25] demonstrated, in two independent samples, that tonic pupil size, an indirect index of locus-coeruleus (LC) / norepinephrine (NE) activation [26], can be used to classify young children with ASD (> 80% correct classification rates) and is associated with level of ASD symptomatology. More recently, we have shown that an indirect measure of central dopaminergic activity, spontaneous eye blink rate [27], is lower in children with ASD [28]. In addition, behavioral eye-tracking measures including the latency of saccadic eye movements and fixation durations have been shown to differ in high-risk infants in both social and non-social paradigms. For example, high-risk infants later diagnosed with ASD become slower at shifting their attention by the end of the first year of life [29, 30] in non-social paradigms and show reduced attention to eyes [31] and decreased attention to social videos [32].

However, it is not yet known whether these biomarkers may accurately distinguish ASD from other children at high-risk for non-ASD neurodevelopmental disabilities. Further, it remains to be determined whether these eye-tracking indices can be successfully measured in the primary care setting. The proposed project builds on early evidence of potential ASD biomarkers by testing whether these data are able to be feasibly acquired in the community-based setting and if these indices can accurately classify children with ASD in a high-risk sample referred for neurodevelopmental evaluation.

Scientific Premise for Aim #3

Converging evidence from studies employing diverse (i.e., genetic, neuroimaging, behavioral) methodologies suggests that ASD is associated with multiple developmental pathways resulting in the emergence of a complex, heterogeneous phenotype. To assist in the diagnosis of ASD and account for this variability, several multivariate approaches using a single neuroimaging modality [33-35] or employing multiple imaging modalities [36] have been used for diagnostic classification. These methods have generally demonstrated positive results; however, as reviewed above, the utility of MRI in the context of early neurodevelopmental evaluation for ASD remains limited. Others have attempted to use multiple behavioral observational and parent/caregiverreport measures to classify ASD [37]. Despite clear group differences, classification of ASD (at 8 months) at the individual level using this approach was only moderately accurate. Recently, Lombardo and colleagues [38] combined neuroimaging and clinical measures to classify language outcomes in children with ASD. These authors showed that fMRI in combination with developmental, adaptive, and ASD symptom severity scores provided good specificity and sensitivity for future language outcome compared to any measure alone. The proposed project aims to adapt this approach by combining novel eye-tracking assays of ASD risk with standardized clinical measures in the context of community-based evaluation to predict diagnostic outcome.

2.0 **Objective(s)**

The overall objective of this proposal is to test an innovative method of ASD diagnosis for young children in the primary care setting, which integrates clinical assessment by general pediatric providers with utilization of eye-tracking biomarkers to improve diagnostic accuracy. Our rationale for this project is that providing evidence for a novel, integrative model of ASD assessment in local communities has the potential to reduce barriers to care, resulting in earlier entry into evidence-based interventions, thereby improving outcomes and decreasing strain on the public health system. Three specific aims guide the proposed research:

Aim #1: Evaluate the diagnostic validity of the Early Evaluation (EE) Hub model of ASD diagnosis in the community-based primary care setting. A team at Indiana University School of Medicine has implemented a community-based early ASD evaluation program at primary-care practices across the state of Indiana. The EE Hubs will refer a consecutive sample of children, ages 14-48 months, for comprehensive expert ASD evaluation. Diagnostic validity will be measured by comparing agreement between the EE Hub and expert ASD-specialist on categorical diagnosis to estimate indices of diagnostic accuracy.

Aim #2: Determine whether biobehavioral markers can reliably differentiate young children with and without ASD in a high-risk community-referral sample. A series of eye-tracking measures (pupil dilation, pupillary light reflex, blink rate) will provide indirect measures of neuromodulator activity (i.e., norepinephrine, acetylcholine, and dopamine, respectively) and social (looking time) and non-social (saccadic latency) attentional processes. Differences in metrics between children with and without ASD will be compared to validate potential biomarkers.

Aim #3: Determine whether a combination of clinical and biobehavioral measures can be used to accurately predict ASD diagnostic outcome in a high-risk sample of young children evaluated in the primary care setting. We will evaluate the predictive efficacy of clinical measures and biobehavioral markers for accurate ASD diagnostic classification, and further determine whether a multimodal combination of clinical and biobehavioral measures may potentially provide a more promising method for ASD diagnostic classification in the primary care setting. Classifier analysis for diagnostic outcome will be completed.

3.0 Outcome Measures/Endpoints

Standardized Clinical Measures

Toddler ASD Interview for Caregivers: Standard caregiver interview questions to assess for DSM-5 [39] [6]ASD criteria in toddlers. To be administered and ratings completed by the expert ASD specialist following the clinical interview. Additional ratings based on observation of the child throughout the evaluation will be completed by the expert ASD specialist.

Autism Diagnostic Observation Schedule, Second Edition (ADOS-2) [40]: The ADOS-2 is a semistructured standardized measure of social communication, play, and restricted and repetitive behaviors for individuals, ages 12 months and up, with varying developmental and language levels. Algorithm scores are compared with cutoff scores to yield a diagnostic classification (i.e., Autism, Autism Spectrum, or Non-spectrum; or Range of Concern for the Toddler Module). The comparison score allows for examination of an individual's overall level of ASD-related symptoms in relation to those of other same-aged children diagnosed with ASD who have similar language skills.

Mullen Scales of Early Learning (MSEL) [41]: The MSEL is a brief and reliable measure of cognitive ability in children from birth to 68 months of age, and includes five scales: Gross Motor, Visual Reception, Expressive Language, and Receptive Language. T-scores for each scale and an Early Learning Composite standard score are produced.

Vineland Adaptive Behavior Scales, Third Edition (VABS-3) [42]: The VABS-3 is a parent/caregiver interview that assesses a child's adaptive skills across the domains of Communication, Daily Living Skills, Socialization, Motor Skills, and Maladaptive Behavior.

Subdomain scaled scores, domain standard scores, and an Adaptive Behavior Composite standard score are derived from the measure.

Sensory Processing Assessment [43]: An abbreviated version of the Sensory Processing Assessment will be used to measure behavioral sensory responses to tactile, auditory, and/or visual information during play.

Biomarker Measures

An SR Research EyeLink Portable Duo remote eye-tracking system will be used to measure eye movements and pupil diameter. Four separate paradigms will be administered totaling 8-10 minutes in duration. Eye-tracking measures will include pupil dilation, percentage looking time, and latency to initiate saccadic eye movements.

Caregiver Report Measures

EAE Hub Satisfaction Questionnaire: Brief caregiver report questionnaire to assess caregiver satisfaction with Early Evaluation Hub clinical diagnostic evaluation visit.

Demographic and Background History Questionnaire: Brief caregiver-report questionnaire that collects information on child's race and ethnicity, family income, caregiver education level, and child medical history.

ASD Risk Questionnaire: Brief caregiver-report questionnaire to assess for and quantify potential environmental risk factors for ASD.

Child Behavior Checklist (CBCL1.5-5) [44]: The CBCL obtains caregiver ratings for 99 problem behaviors in children ages 1.5 through 5 years. Items are scored on the following syndrome scales: Emotionally Reactive, Anxious/Depressed, Somatic Complaints, Withdrawn, Attention Problems, Aggressive Behavior, and Sleep Problems. Items are also scored on the following DSM-oriented scales: Affective Problems, Anxiety Problems, Pervasive Developmental Problems, Attention Deficit/Hyperactivity Problems, Stress Problems, Autism Spectrum Problems, and Oppositional Defiant Problems.

Intervention Service Questionnaire: Brief caregiver report questionnaire that gathers information on interventions and services a child may be enrolled in, intervention duration and intensity, caregiver perceived progress, and barriers faced in service enrollment.

See Section 5.0 for study procedures (including how measures will be collected).

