6.0 Enrollment/Randomization

Subjects will be identified by the EE Hubs. Parent/caregiver(s) of a consecutive sample of children (ages 14-48 months) will be given a study information brochure and asked if they are interested in learning more about the study. If interested, parent/caregiver(s) will fill out a contact information sheet, which will be sent to the research coordinator. The research coordinator will contact the parent/caregiver(s) by phone/email to provide additional information about the study. If the parent/caregiver(s) agree to participate, the research coordinator will schedule the research visit. Written informed consent and authorization (to share evaluation results between EE Hub, child's primary care, and research team will be obtained at the time of the appointment.

Blinded Evaluation Process: Because the family will have received an initial diagnosis for their child during the evaluation at the EE Hub, there is risk for the family to share this information with the blinded ASD specialist, thereby introducing bias into the final diagnostic decision. In order to mitigate this bias, families will be informed on several occasions (i.e., at the time of referral, during the consenting process, and by the blinded ASD-specialist) that they are not to share their child's EE Hub diagnosis with the ASD specialist.

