Informed consent will occur at the start of the research visit. The parent/caregiver (or current legal guardian) will sign the HIPAA authorization form allowing the EE Hub to share evaluation data (MCHAT or MCHAT-R/F, ASQ-3, and STAT scores), diagnosis, and diagnostic certainty ratings with the study personnel and for the study personnel to provide research evaluation data back to the participant's primary care physician and EE Hub physician. The research visit will last for a duration of 3 hours, during which an ASD specialist (and/or other study personnel under the direction of an ASD specialist) will: 1) conduct a semi-structured clinical interview to gather developmental history, DSM-5 symptoms of ASD, and related medical/ neurodevelopmental information, 2) administer the Autism Diagnostic Observation Schedule-2 and Mullen Scales of Early Learning to the child, 3) administer the Vineland Adaptive Behavior Scales (Vineland-II) to the parent/caregiver of the child, 4) request that the parent/ caregiver complete symptom/behavior rating scales and a brief demographic questionnaire if not completed prior to the visit (as described above). The ASD specialist will also complete the same

diagnostic certainty form (as above), 5) complete a brief sensory processing assessment (SPA), and 6) collect a brief sample of eye-tracking data (~15mins; see below).

Eye-tracking data will be collected using a remote eye-tracking system (SR Research, Eyelink Portable Duo), which is placed in front and below the stimulus presentation monitor. Eye movements and pupil diameter will be collected while participants view a series of pictures and movies. The modular system is completely non-invasive with no hardware on or touching participants (only a small sticker is placed on their forehead). A camera monitors eye movements while a second scene camera monitors head movements, allowing eye-tracking to take place without a chin rest or bite bar. Children will be asked to sit on a chair or on their caregiver's lap and will face a computer monitor. After the sticker is applied to participant's forehead and brief calibration completed, visual stimuli will be presented on a laptop computer monitor that is placed at approximately 60cm from the participant. Brightness will be at a comfortable viewing level. The eye tracking portion of the visit will last approximately 15 minutes. All study procedures and data collection will occur at the EE Hub sites.

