Participants will be compensated with a gift card in the amount of \$25 per hour of completed research testing (up to a maximum of \$75). The average length of the evaluation is estimated to be 3 hours. This hourly amount includes any travel related expenses. If participants choose to withdraw from the study, they will be compensated for the length of their participation (at the above rate of \$25 per hour).

Results of the evaluation will be provided to the child's parent/caregiver(s) verbally following the evaluation. A brief report summarizing results of the evaluation and research diagnosis will be provided to the child's parent/caregiver(s), primary care physician, and the EE Hub physician (as appropriate with authorization). In cases where the diagnosis differs between the EE Hub and ASD specialist, the ASD specialist will contact the child's primary care provider and EE Hub provider (when written authorization is provided) by phone, fax, and/or secure email to discuss difference in diagnosis and to help the provider identify next steps in the child's care. The child's family will be offered further consultation by a neurodevelopmental specialist through Riley Hospital for Children neurodevelopmental subspecialists if desired/indicated (provided and billed as a medical service).

Caregivers will be sent a secure electronic link (i.e., Redcap) to complete the Intervention and Service Questionnaire at 3, 6, 12, 18, and 24 months following their research evaluation. If there is no response within 1 week of survey deployment, the research team will reach out by phone to ask caregivers if they would prefer to complete the survey verbally by phone. This survey is estimated to take less than 30 minutes to complete. Caregivers will be reimbursed with a \$15 gift card for every time point a survey is completed.

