compared to validate potential biomarkers. Logistic regression with diagnosis as the dependent variable and eye-tracking measures as the independent variables will be used to estimate diagnostic accuracy indices (sensitivity, specificity, positive predictive value, and negative predictive value) at various cut-points on the continuous scale of eye-tracking measures, and to estimate the area under the receiver operator curve (AUROC) with the c-statistic. Bivariate logistic regression will be used to test each eye-tracking measure separately to determine its individual diagnostic efficacy; then multivariable logistic regression will be used, with eye-tracking measures simultaneously entered into the model, to test the joint effect of all eye-tracking measures on their combined diagnostic efficacy with respect to the diagnostic accuracy indices, as well as to determine which eye-tracking measures that do not contribute significantly to diagnostic efficacy will be deleted from the multivariable model.

Aim #3: Determine whether a combination of clinical and biobehavioral measures can be used to accurately predict ASD diagnostic outcome: We will evaluate the predictive efficacy of clinical measures and biobehavioral markers for accurate ASD diagnostic classification, and further determine whether a multivariable combination of clinical and biobehavioral measures may potentially provide a more promising method for ASD diagnostic classification of young children in the primary care setting. Classifier analysis for diagnostic outcome (ASD versus non-ASD as determined by the expert ASD-specialist) will be completed using the multivariable logistic regression procedure described above, except the model will contain clinical measures in addition to eye-tracking measures.

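### Nothing separates the specialist's reference diagnosis from the eye-tracking session, or masks eye-tracking processing from the diagnosis, so Aim 2 and Aim 3 accuracy could be biased upward by an unknown amount

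*Combined protocol and SAP*

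**What the plan says.** **Who rates, and from what.** Section 3.0, in the caregiver-interview entry under the clinical measures, states: "Additional ratings based on observation of the child throughout the evaluation will be completed by the expert ASD specialist". No part of the visit is excluded.

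**Who runs the visit.** Section 7.0 gives one numbered list of six tasks for a 3-hour visit. It opens with "an ASD specialist (and/or other study personnel under the direction of an ASD specialist) will" and its last item is "6) collect a brief sample of eye-tracking data". The specialist may run that item and otherwise directs whoever does.

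**What is blinded.** Section 6.0 tells families that "they are not to share their child's EE Hub diagnosis with the ASD specialist". No other blinding is described. Section 14.0 has records labelled by number with the key held separately, which protects identity but does not hide the diagnosis.

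**When the diagnosis is fixed.** Section 7.0 says "Results of the evaluation will be provided to the child's parent/caregiver(s) verbally following the evaluation". It sets no point at which the diagnosis is recorded relative to eye-tracking.

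**How the two are compared.** In section 12.0, Aim 2 uses "Logistic regression with diagnosis as the dependent variable and eye-tracking measures as the independent variables" without naming whose diagnosis is meant. Aim 3 names it: "ASD versus non-ASD as determined by the expert ASD-specialist".

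**The concern.** Aim 2 asks whether eye-tracking measures separate children with and without ASD, so those measures are the index test and the specialist's diagnosis is the reference. An accuracy study needs each to be obtained without knowledge of the other. Two routes are open here.

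1. **Index test into reference.** If the specialist sees the child look away from social videos and lets this inform the ratings, the marker has helped to set the diagnosis it is then judged against.
2. **Reference into index test.** If calibration effort, trial acceptance or blink and artifact handling is decided by someone who knows the diagnosis, the marker values can drift towards it.

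Either route could raise AUROC, sensitivity and specificity, and a marker of no value could appear validated. Aim 3 uses the same outcome with the same measures in the model, so it inherits the problem. A larger sample does not remove the bias, and contaminated diagnoses cannot be identified afterwards.

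**Working it through.** **1. The plan's own figure (section 12.0).** Inputs: N = 120, two-sided alpha 0.05, ASD proportion 0.34 at the covariate mean and 0.50 one SD away, stated power 83%.

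- OR = (0.50/0.50)/(0.34/0.66) = 1.94, so λ = ln 1.94 = 0.663 and λ² = 0.439.
- Hsieh (1989) formula: δ = [1 + (1+λ²)exp(5λ²/4)]/[1 + exp(−λ²/4)] = 1.84.
- z = [√(120×0.34×0.439/(1+2×0.34×1.84)) − 1.96]/exp(−λ²/4) = (2.82 − 1.96)/0.896 = 0.96, which gives power of 83.2%.

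The stated power reproduces. The point below does not change N, alpha or power.

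**2. The text side by side.**

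| Safeguard | In the documents? |
|---|---|
| Specialist kept out of the eye-tracking session | No; section 7.0 lets the specialist run it |
| That session excluded from the observation ratings | No; section 3.0 sets no limit |
| Diagnosis recorded before eye-tracking | No; the certainty form is mentioned before item 6, but the list is not said to be a time order |
| Specialist blinded to eye-tracking output | No; section 6.0 covers the EE Hub diagnosis only |
| Recordings processed without sight of the diagnosis | No; section 14.0 codes by number only |

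**3. Which markers each route can reach.** Section 2.0 names pupil dilation, pupillary light reflex, blink rate, looking time and saccadic latency. Pupil measures and saccadic latency need the instrument, and no text says that the specialist sees its output. The live route therefore runs mainly through looking time and visible attention. Section 1.0 itself links reduced attention to eyes and to social videos with later ASD, so an expert would know how to read it. The processing route could reach every marker.

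**4. Illustration of size.** Assumptions, none taken from the documents except N and the even split: the marker is standard normal with no true value, and in a fraction q of children the diagnosis is set by whether the marker is above or below its median.

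- AUROC = 0.5(1−q)² + 2×0.75q(1−q) + q² = 0.5 + q/2.
- Difference in means d = 2q√(2/π). Within-group variance s² = 1 − (d/2)². Noncentrality c = √(120×0.25) × d/s².
- P(reject) = Φ(c − 1.96) + Φ(−c − 1.96).

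| q | Children (120q) | AUROC | d | c | P(reject) |
|---|---|---|---|---|---|
| 0 | 0 | 0.500 | 0 | 0 | 5.0% |
| 2% | 2.4 | 0.510 | 0.032 | 0.17 | 5.4% |
| 5% | 6 | 0.525 | 0.080 | 0.44 | 7.2% |
| 10% | 12 | 0.550 | 0.160 | 0.88 | 14.2% |

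Simulated t-tests at n = 120 (400,000 replicates per q) gave 5.0%, 5.4%, 7.2% and 14.0%.

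For a marker with the planned odds ratio of 1.94 per SD and 50% ASD, simulation under the same rule moves AUROC from 0.67 to 0.69 at q = 5% and 0.71 at q = 10%.

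The AUROC shift does not depend on N, while the rejection rate rises with it. At the 300 children for which IRB approval is requested, q = 10% gives c = √75 × 0.1606 = 1.39 and a rejection rate of about 28.5%.

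**The case against.** **The ratings sentence may not mean the eye-tracking session.** It sits in a clinical-measure entry, while eye-tracking has its own biomarker heading in section 3.0. Section 7.0 also uses the word evaluation for the whole visit of about 3 hours. Both readings are open. A reader might infer that the plan instructs the specialist to rate behaviour during eye-tracking; the text permits that but does not establish it.

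**Other staff may do the recording.** True, but they are an option, not a requirement, and they work under the specialist's direction.

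**The specialist has much better evidence.** The paradigms take 8 to 10 minutes (about 15 for the whole eye-tracking portion) of a 3-hour visit that includes the DSM-5 interview, ADOS-2, Mullen and Vineland, and social attention is visible throughout. This stands, and it argues for a small q. At q = 20% the illustration gives an AUROC of 0.60 and a rejection rate of about 42% by simulation, but it has 24 of 120 diagnoses decided by screen behaviour, about 12 of them reversed. A reader might take that as the expected damage; nothing in the documents supports it.

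**Not all markers are exposed.** A reader might infer that all the Aim 2 markers leak live. For pupil measures and saccadic latency the documents give no support for this.

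**Silence on processing may reflect a short protocol.** Section 17.0 refers to IRB documents held elsewhere, which may say more. The protocol itself does not, and coding by number is not masking to diagnosis.

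**Conclusion.** The concern holds as a gap in the safeguards. The documents allow the reference assessor to run or watch the index test and to use what is seen there, and they do not mask processing of the index test from the diagnosis. They do not show that either happens.

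The likely direction is upward for Aim 2 and Aim 3 accuracy, and the amount is unknown. For q from 2% to 10%, a null marker would show an AUROC of 0.51 to 0.55 and be declared significant about 5.4% to 14% of the time at N = 120. These figures rest wholly on an assumed q and an artificial median-split rule, and they describe the live route only; the processing route has not been sized.

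That the Aim 2 diagnosis is the specialist's is inferred from Aim 3 and the design. Aim 1 is not affected in the same way, because eye-tracking plays no part in the EE Hub diagnosis. No stated figure in the plan is wrong. This is a worthwhile, inexpensive improvement and not a fatal flaw.

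**What to change.** 1. **Section 3.0:** state that the specialist's observation ratings and diagnosis exclude the eye-tracking session and its output.
2. **Section 7.0:** where the other personnel already permitted are present, have them run eye-tracking out of the specialist's view. Otherwise, when feasible, record the ratings, diagnosis and certainty form before eye-tracking starts. Note for each child which was done, so that a sensitivity analysis is possible.
3. **Section 12.0 or 13.0:** process recordings and decide trial acceptance with diagnosis and clinical scores masked, and unmask only once the marker file is locked.

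**Cost.** Item 1 is wording. Item 2 reduces scheduling flexibility. The documents do not show that other staff attend every visit, and placing eye-tracking last in a 3-hour visit with children aged 14 to 48 months risks fatigue and lost recordings, which would itself harm Aim 2. That is why the order is set only when feasible. Item 3 costs almost nothing, because records are already coded by number.
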